#### **Part 2:**

#### **Group 1: Placebo**

Participants will receive 3 placebo SC injections from Week 0 through Week 11. At Week 12, participants will cross over to receive 3 bermekimab 350 mg SC injections weekly through Week 31.

**Group 2: Bermekimab 1050 mg SC qw**

Participants will receive 3 bermekimab 350 mg SC injections at Week 0 and every week thereafter through Week 31.

**Group 3: Bermekimab 1050 mg SC qw→q2w**

Participants will receive 3 bermekimab 350 mg SC injections at Week 0 and every week thereafter through Week 11. From Week 12, participants will receive 3 bermekimab 350 mg SC injections every other week thereafter through Week 30. During weeks in which bermekimab is not administered, participants will receive 3 placebo SC injections through Week 31.

**Group 4: Bermekimab 700 mg SC qw→q2w**

Participants will receive 2 bermekimab 350 mg SC injections and 1 placebo SC injection at Week 0 and every week thereafter through Week 11. From Week 12, participants will receive 2 bermekimab 350 mg SC and 1 placebo SC injection every other week thereafter through Week 30. During weeks in which bermekimab is not administered, participants will receive 3 placebo SC injections through Week 31.

Study intervention administration must be captured in the source documents and the case report form (CRF).

For details on rescue medications, refer to Section 6.7.1. For a definition of study intervention overdose, refer to Section 6.6.

Guidelines for study intervention administrations affected by the COVID-19 pandemic are found in Section 10.17.

**6.2. Preparation/Handling/Storage/Accountability****Preparation/Handling/Storage**

Study intervention labels will contain information to meet the applicable regulatory requirements.

Bermekimab (JNJ-77474462) and placebo PFS must be stored at controlled temperatures ranging from 36°F to 46°F (2°C to 8°C) and protected from light according to the product label.

Adalimumab must be stored as indicated on the product-specific labeling.

Refer to the Site IP Binder for additional guidance, including instructions for use, on study intervention preparation, handling, and storage.

## **Accountability**

The investigator is responsible for ensuring that all study intervention received at the site is inventoried and accounted for throughout the study. The study intervention administered to the participant must be documented on the intervention accountability form. All study intervention will be stored and disposed of according to the sponsor's instructions. Study-site personnel must not combine contents of the study intervention containers.

The dispensing of study intervention to the participant, and the return of study intervention from the participant (if applicable), must be documented on the intervention accountability form. Participants must be instructed to return all original containers, whether empty or containing study intervention.

If rescue medication or other medication is also supplied by the sponsor, inclusion of this medication on the intervention accountability form is required. The participants must return unused study intervention to the study site.

Study intervention must be handled in strict accordance with the protocol and the container label and must be stored at the study site in a limited-access area or in a locked cabinet under appropriate environmental conditions. Unused study intervention, and study intervention returned by the participant, must be available for verification by the sponsor's study site monitor during on-site monitoring visits. The return to the sponsor of unused study intervention, or used returned study intervention for destruction, will be documented on the intervention return form. When the study site is an authorized destruction unit and study intervention supplies are destroyed on-site, this must also be documented on the intervention return form.

Potentially hazardous materials such as used ampules, needles, syringes and vials containing hazardous liquids, should be disposed of immediately in a safe manner and therefore will not be retained for drug accountability purposes. The study intervention boxes will be retained for inventory by the sponsor.

Study intervention should be dispensed under the supervision of the investigator or a qualified member of the study-site personnel, or by a hospital/clinic pharmacist. Study intervention will be supplied only to participants participating in the study. Returned study intervention must not be dispensed again, even to the same participant. Study intervention may not be relabeled or reassigned for use by other participants. The investigator agrees neither to dispense the study intervention from, nor store it at, any site other than the study sites agreed upon with the sponsor.

### **6.3. Measures to Minimize Bias: Randomization and Blinding**

#### **Intervention Allocation**

##### ***Procedures for Randomization and Stratification***

Dynamic central randomization will be implemented in this study.

The randomization method will be a minimization procedure with biased-coin assignment for both randomizations, which minimizes the imbalance in the distribution of the number of participants across treatment groups within the levels of each individual stratification factor: investigational site and baseline Hurley stage status (II, III). Based on the algorithm, each participant will be assigned to the treatment group which will produce minimum total imbalance score with a high probability, where the total imbalance score is a weighted average of the imbalance scores for each stratification factor and for the whole study. The Interactive Web Response System (IWRS) will assign a unique treatment code, which will dictate the treatment assignment and matching study drug for the participant.

At first, approximately 150 participants in Part 1 will be randomized to receive bermekimab 1050 mg, adalimumab, or placebo in a 1:1:1 ratio. Enrollment will pause once approximately 150 participants are randomized. Two interim analyses will be performed. The first interim analysis will be performed when approximately 75 participants have completed Week 16 or have terminated study participation. The objective of this interim analysis is to assess whether favorable efficacy is seen in the 1050 mg bermekimab dose group.

The second planned interim analysis will take place once the 150 participants have completed study participation to Week 16 or have terminated study participation. The objectives of the second interim analysis are to assess whether a favorable efficacy is seen in the 1050 mg bermekimab dose group if not determined as favorable at the first interim analysis or confirm the favorable efficacy observed from the first interim analysis, or efficacy is low enough to consider termination of the study or the observed efficacy suggests modification to study.

If favorable efficacy is observed in either the first or the second interim analysis, screening and randomization of participants will resume in Part 2 as planned, with additional participants being randomized to receive bermekimab 1050 mg qw, placebo, bermekimab 1050 mg qw→q2w, or bermekimab 700 mg qw→q2w in a 1:1:2:2 ratio (approximately 25 participants randomized to receive bermekimab 1050 mg qw and placebo, respectively, and approximately 50 participants randomized to receive bermekimab 1050 mg qw→q2w and bermekimab 700 mg qw→q2w, respectively).

However, if 700 mg qw→q2w is not included in Part 2 based on PK results from Part 1, screening and randomization of participants will resume with additional participants being randomized to receive bermekimab 1050 mg qw, placebo, or bermekimab 1050 mg qw→q2w in a 1:1:2 ratio (approximately 25 participants randomized to receive bermekimab 1050 mg qw and placebo, respectively, and approximately 50 participants randomized to receive bermekimab 1050 mg qw→q2w). Thus, if the study continues, a total number of approximately 250 or 300 participants will be enrolled in the study.

Otherwise, enrollment will remain paused while the sponsor considers whether to terminate the study at that point for insufficient efficacy, to resume enrollment as planned, or to resume the study with modification.

The requestor must use his or her own user identification and personal identification number when contacting the IWRS and will then give the relevant participant details to uniquely identify the participant.

### **Blinding**

Active study intervention and placebo will be prepared by an unblinded pharmacist or an unblinded qualified member of the investigational staff. The volume of the placebo will match the volume of the active intervention within each group. Prepared doses will be covered to mask potential visual differences between the active study intervention and placebo. The participants and other site staff members, including the investigator, will be blinded to study intervention allocation through study completion to reduce bias in the assessment of efficacy, safety, and tolerability data.

To ensure that no unintentional unblinding occurs during study intervention administration, at least one qualified site staff member will be designated to perform all SC injections of the IP. This unblinded administrator will have no other contact with the participant during the study and will not discuss the participant's treatment with the participant, the investigator, or other site personnel at any time. The unblinded administrator(s) will be documented in the source documents at each dosing day.

The investigator will not be provided with randomization codes. The codes will be maintained within the IWRS, which has the functionality to allow the investigator to break the blind for an individual participant.

Data that may potentially unblind the intervention assignment (i.e., study intervention serum concentrations, antibodies to bermekimab, and intervention allocation) will be handled with special care to ensure that the integrity of the blind is maintained and the potential for bias is minimized. This can include making special provisions, such as segregating the data in question from view by the investigators, clinical team, or others as appropriate until the time of database lock and unblinding.

Under normal circumstances, the blind should not be broken until all participants have completed the study and the database is finalized. However, selected sponsor personnel will be unblinded for analysis after the Week 12 DBL from Part 2 has occurred. All site personnel and participants will remain blinded to the treatment assignments until the last participant completes Week 36 evaluations and the database has been locked.

The investigator may in an emergency determine the identity of the intervention by contacting the IWRS. While the responsibility to break the intervention code in emergency situations resides solely with the investigator, it is recommended that the investigator contact the sponsor or its designee if possible, to discuss the particular situation, before breaking the blind. Telephone contact with the sponsor or its designee will be available 24 hours per day, 7 days per week. In the event the blind is broken, the sponsor must be informed as soon as possible. The date and reason for the unblinding must be documented in the appropriate section of the eCRF and in the source document. The documentation received from the IWRS indicating the code break must be retained with the participant's source documents in a secure manner.

Participants who have had their intervention assignment unblinded by the investigator will not be eligible to receive further study intervention but should continue complete evaluations specified in the SoA (Section 1.3).

For the planned interim analyses and the DMC, the randomization codes and the translation of randomization codes into intervention and control groups will be disclosed to those authorized and only for those participants included in the interim analysis. For more information, see Sections 9.5 and 9.6.

#### **6.4. Study Intervention Compliance**

Because study intervention will be administered at the investigational site for all randomized participants, intervention compliance will be ensured by site personnel.

When study intervention is administered as an SC injection by qualified staff, the details of each administration will be recorded in the eCRF. These will include date, body location, and time of SC injection.

All visits through Week 32 should occur within  $\pm 3$  days of the scheduled visit throughout the study. Study intervention administration should not occur within 4 days of the last administration of study intervention. If a study visit occurs outside this window, the sponsor should be consulted about how the participant should resume his/her normal dosing schedule relative to the baseline visit (Week 0).

Information regarding study intervention administrations that are administered outside of the scheduled windows or missed will be recorded. Source data will be reviewed and compared with the data entries on the eCRFs to ensure accuracy. Although it is understood that intervention may be interrupted for many reasons, compliance with the intervention schedule is strongly encouraged.

#### **6.5. Dose Modification**

No treatment/dose adjustment will be permitted through the study.

#### **6.6. Treatment of Overdose**

For this study, any dose of bermekimab greater than the highest dose at a single dosing visit will be considered an overdose. The sponsor does not recommend specific treatment for an overdose.

In the event of an overdose, the investigator or treating physician should:

- Contact the Medical Monitor immediately.
- Closely monitor the participant for AE/serious adverse event (SAE) and laboratory abnormalities.
- Document the quantity of the excess dose as well as the duration of the overdosing in the CRF.

Decisions regarding dose interruptions or modifications will be made by the investigator in consultation with the medical monitor based on the clinical evaluation of the participant.

## 6.7. Concomitant Therapy

Prestudy therapies administered up to 30 days before first administration of study intervention must be recorded at screening.

Concomitant therapies must be recorded throughout the study from Week 0 through Week 36 or continuing until 5 weeks after the last administration of study intervention. Concomitant therapies on randomized participants should also be recorded beyond that point only in conjunction with SAEs that meet the criteria outlined Section 8.3.1.

When considering use of locally-approved (and including emergency use-authorized) COVID-19 vaccines in study participants, follow applicable local vaccine labelling, guidelines, and standards of care for participants receiving immune-targeted therapy. For study participants receiving a locally-approved (and including emergency use-authorized) COVID-19 vaccine, in order to help identify acute reactions potentially related to COVID-19 vaccine, it is recommended where possible that vaccine and study drug be administered on different days, separated by as large an interval as is practical within the protocol.

All therapies (prescription or over-the-counter medications, including vaccines, vitamins, herbal supplements; non-pharmacologic therapies such as electrical stimulation) different from the study intervention must be recorded in the CRF. If a medication is temporarily discontinued because of abnormal laboratory values, side effects, concurrent illness, or the performance of a procedure, the change and reason for it should be clearly documented in the participant's medical records. Modification of an effective preexisting therapy should not be made for the explicit purpose of entering a participant into the study.

The sponsor must be notified in advance (or as soon as possible thereafter) of any instances in which prohibited therapies are administered.

### 6.7.1. Rescue Medication

Rescue interventions are not allowed during the study. However, in the event that a particularly painful HS lesion occurs that necessitates an acute intervention, investigators will have the option to perform protocol-allowed interventions starting at Week 2. Otherwise, the use of rescue interventions should be avoided during the study.

When necessary, 2 types of interventions may be used as rescue:

- Injection with intralesional triamcinolone acetonide suspension (at a concentration of 10 mg/mL, up to 0.5 mL)
- Incision and drainage of the lesion

If incision and drainage is performed, the required over-the-counter soap and water or antiseptic wash should continue to be used. New systemic and topical therapies following incision and drainage (including antibiotics) are prohibited. Concomitant use of wound care dressings is allowed; however, options are limited to alginates, hydrocolloids, and hydrogels. Participants should continue using any ongoing oral and topical therapies (as described in Section 6.7) during the study.

Concomitant therapies associated with the lesion intervention(s) must be captured in the source documentation and on the appropriate eCRF.

The number of interventions allowed during the 32 weeks of the study is defined by the number of lesions present at baseline:

- For participants with an AN count of 5-8 at baseline, it is permissible to perform a single lesion intervention. If a participant with 5-8 lesions at baseline, requires more than 1 intervention during the study, then he or she must be discontinued from IP but continued for follow-up for approximately 5 weeks after last administration of IP.
- For subjects with an AN count >8 at baseline, a total of 2 rescue interventions are permissible. An intervention can occur maximally on 2 different lesions at the same visit or on the same lesion at 2 different study visits. The same lesion cannot be treated 2 times at the same visit. If a participant requires more than 2 interventions during the study, then he or she must be discontinued from IP but continued for follow-up for approximately 5 weeks after last administration of study intervention.

All study visit evaluations must occur before any interventions are performed. Any lesion that undergoes an intervention will be documented in the source.

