**6.7.5. Prohibited Therapy**

Participants who initiate the following treatments during study participation must have their study intervention discontinued:

- Phototherapy (PUVA and/or UVB)
- All biologic therapy with a potential therapeutic impact on the disease being studied, including but not limited to the following:
  - TNF  $\alpha$ blockers (adalimumab, etanercept, certolizumab, infliximab, golimumab)
  - IL 1 blockers (anakinra, canakinumab, rilonacept)
  - IL 6 blockers (tocilizumab, sarilumab)
  - IL 23 blockers (ustekinumab, guselkumab, tildrakizumab)
  - IL 17 blockers (secukinumab, ixekizumab, brodalumab)
  - CD20- directed cytolytic antibody (rituximab)
  - Inhibitor of B-Lymphocyte stimulator-specific (belimumab)
  - Integrin receptor antagonist (natalizumab)
  - Inhibitor of T cell activation (abatacept)
  - JAK inhibitor (systemic and topical)
- Any investigational agents for the treatment of HS.
- Any other systemic drug therapies for HS, including but not limited to MTX, cyclosporine, and retinoids.

- Concomitant use of oral antibiotic therapy for HS or inflammatory disorders. Systemic antibiotic use (including oral) is allowed for the treatment of AEs other than a worsening of HS.
- Oral or injectable corticosteroids for the treatment of HS, except for protocol-allowed intralesional rescue therapy as outlined in Section 6.7.1.
- Surgical or laser intervention for an HS lesion except as outlined in Section 6.7.1.

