## 5.3. Primary Endpoint Analysis

### 5.3.1. Definition of Endpoint(s)

The primary efficacy endpoint is the proportion of participants achieve a HiSCR50 at Week 16 in Part 1. HiSCR50 is defined as a  $\geq 50\%$  reduction in inflammatory lesion AN count (sum of

abscesses and inflammatory nodules), and no increase in abscesses and draining fistulas in HS compared with the lesions counted at baseline.

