### 5.3.2. Estimand

An estimand is a precise definition of the primary targeted treatment effect defined by the following 5 attributes: Study Intervention, population, variable (endpoint), intercurrent events (ICEs) and corresponding strategies, and population-level summary.

**Primary Trial Objective:** to evaluate the efficacy of bermekimab in participants with moderate to severe HS.

**Estimand Scientific Question of interest:** What is the proportion of participants considered to have benefited from bermekimab versus placebo assessed by the HiSCR50 at Week 16 in Part 1, administered together with the protocol allowed background standard-of-care medication.

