#### 5.3.2.1. Primary Estimand (Composite Estimand)

- **Study intervention:**
  - Bermekimab 1050 mg
  - Placebo
- **Population:** adult participants with moderate to severe HS
- **Variable/endpoint:** Response binary variable, where a responder is defined as a participant achieving an HiSCR50 response at Week 16 in Part 1 without experiencing any of the ICEs in categories 1-2 as outlined below prior to the Week 16 visit.

Intercurrent Events (ICEs)	Analysis Strategy for Intercurrent Events
1. Discontinuation of study intervention due to lack of efficacy, an AE of worsening of HS	Composite Strategy: Participants with these intercurrent event are considered as HiSCR50 non-responders after these events, and prior to Week 16, as reflected in variable definition.
2. Initiation of a protocol-prohibited medication or therapy during the study that could improve H S	
3. Discontinuation of study intervention for reasons other than ICE 1	Treatment Policy: observed data will be used regardless of whether or not this intercurrent event had occurred.

Note: For participants experiencing multiple ICEs, ICE 2 will override ICE 3.

The composite strategy assesses the treatment effects not only based on the variable measurements, but also based on ICEs. This estimand acknowledges that having an ICE in categories 1-2 is an unfavorable outcome. For participants experiencing an ICE in category 3, the treatment policy

strategy considers the occurrence of ICE 3 irrelevant in defining the treatment effect, and any data observed after the associated ICE event will be used for the analysis.

**Population level summary:** Difference in the proportions of participants achieving an HiSCR50 response at Week 16 between the bermekimab 1050 mg and placebo intervention groups.

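### Should the lesion procedures that the protocol allows be named as an intercurrent event for HiSCR50, with a rule for counting the treated site?

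*Protocol*

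**What the plan says.** Protocol section 6.7.1 opens by ruling out rescue, then makes an exception where "a particularly painful HS lesion occurs that necessitates an acute intervention". In that case "investigators will have the option to perform protocol-allowed interventions starting at Week 2": injecting triamcinolone into the lesion, or incising and draining it. The number is capped: "For participants with an AN count of 5-8 at baseline, it is permissible to perform a single lesion intervention", and two are allowed when the baseline AN count is above 8. Needing more than the cap means stopping study drug. Assessments at a visit come before any procedure at that visit.

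Section 6.7.5 of the protocol lists prohibited therapy and carves these procedures out twice. Injected steroid for HS is prohibited "except for protocol-allowed intralesional rescue therapy as outlined in Section 6.7.1", and the last item on the list reads "Surgical or laser intervention for an HS lesion except as outlined in Section 6.7.1".

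SAP section 5.3.2.1 has three intercurrent events. ICE 1 and ICE 3 are discontinuations of study drug. ICE 2 is "Initiation of a protocol-prohibited medication or therapy during the study that could improve" HS. ICE 1 and 2 are scored as non-response; ICE 3 is handled by treatment policy. The scientific question in SAP section 5.3.2 concerns bermekimab versus placebo "administered together with the protocol allowed background standard-of-care medication".

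HiSCR50 (SAP section 5.3.1) needs an AN reduction of at least 50% and "no increase in abscesses and draining fistulas in HS compared with the lesions counted at baseline". The lesion-count definitions (protocol section 8.1.3, SAP section 5.4.2.2) list the lesion types and give no rule for a treated lesion.

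**The concern.** A procedure within the cap, with study drug continued, is none of ICE 1 to 3, so no strategy is assigned to it by name. The estimand is labelled composite, and a reader might expect rescue to count against response. Here it does not: the Week 16 counts are taken as they stand, in both the primary and the supplementary analysis (SAP section 5.3.4).

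HiSCR50 can turn on one lesion. A new abscess makes a participant a non-responder; once drained, it may not. Whether the drained site is then recorded as nothing, as an abscess or as a draining fistula is left to the rater. Some responders in the primary result could therefore owe their status to a procedure, and the planned outputs would not show how many. SAP Appendix 5 lists only ICE 2 users and summarises concomitant medication by ATC class and arm. If procedures were common and unequal between arms, the treatment difference would partly reflect them.

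**Working it through.** **1. The plan's own figure.** Inputs from protocol section 9.2: 50 per arm, 25% versus 50%, two-sided alpha 0.10, stated power 83%.

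- Pooled SE = sqrt(2 x 0.375 x 0.625 / 50) = 0.0968.
- Unpooled SE = sqrt(0.1875/50 + 0.25/50) = 0.0935.
- Power = Phi[(0.25 - 1.645 x 0.0968) / 0.0935] = Phi(0.97) = 83.4%. The stated figure reproduces.
- 90% CI half-width = 1.645 x 0.0935 = 15.4 points.

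**2. Can one procedure decide HiSCR50?** Take a baseline of 8 nodules, no abscesses and no draining fistulas (AN 8, one procedure allowed). Later there are 3 nodules and 1 new abscess.

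- Untreated: AN 4, a 50% reduction, but abscesses 1 > 0. Non-responder.
- Drained, counted as no lesion: AN 3, no increase. Responder.
- Drained, counted as a draining fistula: AN 3, but fistulas 1 > 0. Non-responder.

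The 50% threshold is a second route. With 1 abscess and 4 nodules at baseline, AN 3 fails and AN 2 responds. So the answer is yes for an individual.

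Two rules limit this. With two new abscesses in the AN 8 example, one allowed procedure leaves 1 > 0 and the participant still fails, so the cap does restrict what can be cleared. And because assessment precedes treatment, a procedure at the Week 16 visit cannot alter the Week 16 count; only procedures from Week 2 up to that visit can.

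**3. Could one participant matter to the test?** Unstratified z-test, 50 per arm, 12 placebo responders:

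- 19 bermekimab responders: z = 0.14 / sqrt(0.31 x 0.69 x 2/50) = 1.51, p = 0.130.
- 20 bermekimab responders: z = 0.16 / sqrt(0.32 x 0.68 x 2/50) = 1.72, p = 0.086.

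One reclassification can cross 0.10, but only near the boundary, as with any binary endpoint.

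**4. Trial-level size.** The documents give no rate of procedure use, so everything here is assumed. Let r be the share of an arm with a procedure before Week 16 and p the HiSCR50 rate among them. Observed scoring minus non-response scoring changes the treatment difference by r(bermekimab) x p(bermekimab) - r(placebo) x p(placebo). Results in points:

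| Rescue, placebo / bermekimab | p = 25% / 50% | p = 35% / 75% | p = 30% in both |
|---|---|---|---|
| 10% / 10% | +2.5 | +4.0 | 0 |
| 20% / 10% | 0 | +0.5 | -3.0 |
| 30% / 10% | -2.5 | -3.0 | -6.0 |
| 10% / 20% | +7.5 | +11.5 | +3.0 |

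For example, 10% / 20% with 35% / 75%: 0.20 x 75 - 0.10 x 35 = 15 - 3.5 = +11.5. All values halve if rescued participants respond at half these rates.

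Power under assumed shares of each arm turned into responders by a procedure: 5% in both arms, 82%; 5% on placebo only, 66%; 5% on bermekimab only, 93%.

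The sign depends on which arm uses more procedures and on how rescued participants respond. The table compares two legitimate scorings; it does not measure error in either. The probability that a given procedure flips a response cannot be derived. It needs the chance that the AN condition is met and the chance that the abscess would have persisted to Week 16. The design rates are HiSCR50 rates that already include the no-increase conditions, and no persistence figure is given.

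**5. Is the calculation undefined?** No. A count taken after a procedure is not missing, so the non-responder imputation in SAP section 5.3.3 does not touch it. No ICE rule touches it either. The observed count is used, and two analysts working from the SAP would get the same number.

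**The case for a change.** The best case for a change is that a defined calculation is not a defined estimand. The SAP question speaks of background medication. An acute procedure for a painful lesion is hardly background, and incision and drainage is not a medication. A sentence naming treatment policy, a table by arm and one sensitivity analysis would cost little, since protocol section 6.7 already requires all therapies to be recorded in the CRF.

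Much of this stands. The strategy is implied and not written, no rule says how a treated site is counted, and the ATC summary may show triamcinolone by arm but is unlikely to capture drainage or link it to response. How a discontinuation for exceeding the cap is classified among the ICEs is also not settled by the documents.

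It does not carry a change, for four reasons. First, the implied handling matches how the SAP treats other permitted care: as-needed analgesics for HS pain, including tramadol, are also analysed as observed. That applies equally to the HSSD-24h pain score, a weekly average that both kinds of care can affect. Second, the alternative is a trade-off and no clear improvement: non-response scoring penalises participants who would have responded anyway. Third, the SAP was written after the futility criterion was met and the study stopped, so wording added to it cannot settle how raters had classified drained sites. Fourth, none of the additions would alter the primary analysis.

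**Conclusion.** The gap in wording is real, and a single procedure can decide an individual's response. It does not make the plan wrong. The exemption in protocol section 6.7.5, the ICE list and the missing-data rule together lead to one result, with observed Week 16 counts used. That is a defensible treatment-policy reading, and analysts would fill the gap that way without instruction.

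The effect is limited to one or two lesions per participant and to procedures between Week 2 and the Week 16 visit. At trial level, the choice of scoring moves the difference by -6.0 to +11.5 points over the assumed rescue and response rates, against a half-width of 15.4 points at 50 per arm. The real interval is likely wider, because the mFAS drops participants whose projected Week 16 visit falls after the termination decision. Frequency, size and direction cannot be obtained from the documents.

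If procedures prove common or uneven when the data are seen, the study report can describe them from the recorded therapies. That needs no change to the plan.
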